7.7 Clinical Data Collection

Information about subject demographics, eligibility requirements, procedure, specific concomitant medications as well as complications and/or device related adverse events will be collected on the eCRFs provided by the Sponsor. The eCRFs should accurately reflect data contained in the subject's medical records (i.e. source documents).

8 Adverse Events

Subject complications will be monitored via the reporting of device related adverse events occurring from the time of enrollment (insertion of guidewire into radial artery) through study completion (withdrawal for any reason or completion of 365-day follow-up visit). For this registry, adverse events collected will be limited to any events possibly, probably or definitely related to a Terumo device, as described below in Section 8.2.

Where an adverse event has, by its nature, a prolonged course, the event will be considered a single event and not multiple events.

The investigator is not required to actively seek adverse events from a subject once a subject has exited the study. If the investigator learns of any device related adverse event at

any time after a subject's exit from the study, the investigator should promptly report it to the Sponsor.

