3.2.1 Primary Evaluations

Primary Safety Evaluation:

The primary safety evaluation is freedom from major adverse events and radial access complications within 30 days post-procedure.

Major Adverse Events are defined as:

1. Death
2. MI
3. Stroke

Radial Access related complications are defined as:

1. Radial artery occlusion
2. Hand ischemia
3. Arteriovenous fistula
4. Pseudoaneurysm
5. Any complication requiring surgical and/or endovascular intervention within 30 days of index procedure.

Primary Efficacy Evaluation:

The primary efficacy evaluations are procedural success and technical success.

1. Procedural success is defined as completing the planned procedure without femoral access bailout.
2. Technical success is defined as delivery of HydroPearl to the target vessel and slowing the blood flow with microsphere embolization. Embolization may be confirmed clinically or radiologically at the discretion of the site investigator.

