5.7 Subject Withdrawal

Subject participation in the study is voluntary. Subjects may withdraw their consent from participation in the study at any time. A subject may withdraw completely or may withdraw but leave the authorization to access their medical records in compliance with local regulations. Should a subject leave the study for any reason, the investigator will document the reason if known, and report in the study database.

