8.3 Follow-up of Adverse Events

All device related adverse events observed from the time of enrollment throughout the duration of the study must be reported on the eCRF. All device related adverse events will be followed until resolution or stabilization of symptoms through study completion and/or the subject withdraws consent. Resolution means that the subject has returned to a baseline state of health. Stabilization means that the investigator does not expect any further improvement or worsening of the adverse event.

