13.2.1 Study Visit

The Study Visit Day 0 is the date of the index procedure. Day in study will be calculated relative to the index procedure as follows:

$$\text{Study Day} = \text{Assessment Date} - \text{Index Procedure Date}$$

For each subject, duration in study will be based on last study contact date which is the latest date of all follow-up visits, assessments, adverse event onset or resolution, and study exit including date of death.

Duration variables will be calculated as follows:

$$\text{Duration Days} = \text{End Date} - \text{Start Date}$$

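### Section 5.7 lets record access outlast withdrawal, but Section 8 ends active event collection at any withdrawal, and the protocol does not say the retained access will be used to establish 30-day safety status

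*Combined protocol and SAP*

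**What the plan says.** Section 5.7 (Subject Withdrawal) provides for two kinds of withdrawal: "A subject may withdraw completely or may withdraw but leave the authorization to access their medical records in compliance with local regulations". On exit it asks for one thing: "Should a subject leave the study for any reason, the investigator will document the reason if known, and report in the study database".

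Section 8 (Adverse Events) sets the collection period for device related events. It runs from guidewire insertion "through study completion (withdrawal for any reason or completion of 365-day follow-up visit". Subjects who leave record access in place are not excepted. The section adds: "The investigator is not required to actively seek adverse events from a subject once a subject has exited the study". It does keep a passive route, because a device related event that the investigator hears of after exit should be reported promptly to the sponsor.

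Section 8.3 follows events that are already open "through study completion and/or the subject withdraws consent".

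Four other sections bear on the point:
- Section 3.2.1: "The primary safety evaluation is freedom from major adverse events and radial access complications within 30 days post-procedure". The components are death, MI, stroke and five kinds of radial access complication.
- Section 5.8 lists a serious or severe adverse event, or an unanticipated adverse device effect, among the reasons for ending participation.
- Section 13.5 restricts analysis to observed cases, with the amount of missing data reported.
- Section 13.1 justifies the sample size by a probability above 80% of seeing at least one major complication in 100 evaluable patients, if the true rate is 1.6% or more.

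**The concern.** The protocol obtains a permission and then gives it no stated use. A subject who stops attending on day 10 but leaves the records open is, under Section 8, past study completion. If a device related pseudoaneurysm is found at the same hospital on day 20, nobody is asked to look for it, although the subject has agreed that the site may look.

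Open events have the same problem. Hematoma is not a primary safety component, but a complication that needs surgical or endovascular intervention within 30 days is. Suppose a hematoma judged possibly device related is open when the subject withdraws on day 10. Section 8.3 no longer follows it, so a later intervention that would make it a primary event can be missed.

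Primary safety is a short-term outcome with few expected events, so one subject of unknown status matters more than in a trial with a common endpoint. Exit need not be unrelated to risk, and an observed-case analysis does nothing to compensate.

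**Working it through.** **1. The sections side by side.**

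| Question | Section | Answer |
|---|---|---|
| May records be read after withdrawal? | 5.7 | Yes, if the subject leaves authorization in place and local regulations allow |
| What must be recorded at exit? | 5.7 | The reason, if known |
| When does active event collection end? | 8 | At any withdrawal, or the 365-day visit |
| When does follow-up of open events end? | 8.3 | At study completion and/or withdrawal of consent |
| What continues after exit? | 8 | Passive reporting of device related events |
| How are subjects of unknown status analyzed? | 13.5 | Observed cases only |

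No row uses the permission in the first row to establish 30-day status.

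**2. The plan's own figure.** Inputs from Section 13.1 are n = 100 and rate p = 0.016. The probability of at least one event is 1 − (1 − p)^n.

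1 − 0.984^100 = 0.8007, or 80.07%. The stated figure reproduces.

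**3. Slack in that figure.** The smallest n that reaches 80% is ln(0.20)/ln(0.984) = 99.8, so 100. Sections 2.2 and 4.2 plan 100, or up to 100, enrolled subjects and state no allowance for loss. The documents give no withdrawal rate, so the losses below are assumptions.

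| Evaluable n | Probability of at least one event at 1.6% | Rate detectable with 80% probability, 1 − 0.2^(1/n) |
|---|---|---|
| 100 | 80.07% | 1.60% |
| 99 | 79.7% | 1.61% |
| 98 | 79.4% | 1.63% |
| 95 | 78.4% | 1.68% |
| 90 | 76.6% | 1.77% |

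One unevaluable subject takes the figure just below 80%. The decline after that is gradual.

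**4. Effect on the reported percentage.** Assume 100 treated subjects, of whom 5 leave before day 30 and are dropped, with 2 events seen in the other 95. Observed-case freedom from events is 93/95 = 97.9%. With all 100 known, it depends on the unseen events:
- none: 98/100 = 98.0%
- one: 97/100 = 97.0%
- two: 96/100 = 96.0%

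The observed-case figure is then between 0.1 points too low and 1.9 points too high.

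**5. How likely an unseen event is.** If those who leave carry only the 1.6% rate, 5 subjects have 5 × 0.016 = 0.08 expected events, and the chance of at least one is 1 − 0.984^5 = 7.7%. For 10 subjects it is 0.16 expected events and 1 − 0.984^10 = 14.9%. A larger effect requires exit to be related to risk. Section 5.8 makes that possible, but the documents do not show how often it happens.

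**The case against.** The strongest reply is that this is a descriptive, on-label registry with no hypothesis test. Only subjects who leave between guidewire insertion and their 30-day assessment are affected, probably few, and Section 8 already asks for post-exit device related events to be reported. The consent form and eCRFs are not available here and may say how retained access is used. All of this stands. It limits the point to what the protocol text does not say and keeps the size modest. It does not remove the gap, because passive reporting depends on the investigator happening to hear of an event.

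A reader might also infer several stronger things that the documents do not support:
- **That post-exit 30-day data are not collected at all.** Passive reporting of device related events survives exit.
- **That Sections 5.7 and 8 contradict each other.** One grants a permission and the other sets a collection period. The permission is unused.
- **That withdrawal is why an unrelated stroke would be missed.** Section 8 limits collected adverse events to those at least possibly related to a Terumo device, for every subject. Such a stroke falls outside it even in a subject who stays. That is a separate limit.
- **That follow-up time is distorted.** Section 13.2.1 ends duration in study at "the latest date of all follow-up visits, assessments, adverse event onset or resolution, and study exit including date of death", so an event learned of after exit might seem to lengthen follow-up only for those with events. No section says that such an event enters the analysis data or sets a Kaplan-Meier censoring date, and Section 13.2 does not name primary safety as a time-to-event endpoint.
- **That the event rate could be badly understated.** Placing one event among five assumed withdrawals produces a large relative change, but that rests on the assumption. At the planning rate, five subjects have a 7.7% chance of any event.

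**Conclusion.** The point holds in a limited form. Active event collection and follow-up of open events both end at any withdrawal, and the protocol text does not direct sites to use the record access that Section 5.7 allows a subject to leave in place. Subjects who exit before day 30 can therefore be lost from the primary safety evaluation although their status could be read with their permission.

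The size is small but not nil. The stated detection probability holds at 100 evaluable subjects with a margin of 0.07 points and fails at 99. This assumes that a subject without 30-day status counts as unevaluable. It also takes 1.6% from Section 13.1, where it refers to major complications and not to the composite in Section 3.2.1. The effect on the reported percentage depends on the number of early exits and the unseen events among them, and the documents give neither. It would be wrong to call the safety results uninterpretable on this ground. The change is recommended because it is cheap and recovers data the subject has already released.

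**What to change.** 1. In Sections 5.7, 8 and 8.3, state that where record authorization remains, the site takes 30-day status for the primary safety components (death, MI, stroke and the radial access complications) from the medical record, within local regulations.
2. Apply the same event scope as for retained subjects. If only device related events count for those who stay, the same must hold for those who leave. Otherwise the two groups are ascertained differently.
3. Record the type of withdrawal on the exit eCRF: complete, or visits only.
4. Report how many subjects exited before day 30, by type of withdrawal, next to the primary safety result.

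The cost is a few sentences, one eCRF field and one or two chart reviews for a few subjects. The reported event rate may rise slightly. Record review cannot help after complete withdrawal, or when care was given elsewhere and is not in the site's record. The count in item 4 shows how much remains unknown.

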Primary Study Evaluations	
1. Procedural success defined as completing the planned procedure without femoral access bailout2. Technical success defined as delivery of HydroPearl to the target vessel and slowing the blood flow with microsphere embolization.3. Freedom from Major Adverse Events within 30 days of procedure, defined as:
a. Deathb. MIc. Stroke4. Freedom from radial access related complications at 30 days, defined as:
a. Radial artery occlusion (reverse Barbeau and/or Ultrasound, per site standard of care)b. Hand ischemiac. Arteriovenous fistulad. Pseudoaneurysme. Any complication requiring surgical and/or endovascular intervention within 30 days of index procedure
Additional Evaluations	
1. Incidence of Radial Artery Occlusion Complications at any time
a. Arteritis

	
b. Cellulitisc. Ecchymosisd. Pain at puncture sitee. Hematoma 
2. Quality of Life and Health Economics3. Procedural endpoints:
a. Blood lossb. Patient radiation exposurec. Contrast volumed. Time to hemostasise. Total procedural timef. Time to dischargeg. Operative timeh. Radial cocktail components and frequency of administration4. Access endpoints:
a. Radial artery spasmb. Time to dischargec. Radial access pain VAS5. Closure endpoints
a. Time to hemostasisb. Time to ambulation
Procedure Evaluations	
1. Tumor type2. Number and size of tumors / fibroids3. Post embolization syndrome4. UFE:
a. If post-op MRI is obtained per standard of care: Effectiveness of HydroPearl measured by MRI.
i. Infarction is characterized by complete (100%), 90-99%, 50-89%, or less than 50%.ii. Uterine Volumeiii. Dominant Fibroid Volumeb. EQ-5Dc. UFS-QoLd. Return to normal activitiese. Pain VASf. Symptoms including bleeding and bulkg. Pregnancy intention and occurrence5. Prostate Artery Embolization:
a. IPSS with Quality of Lifeb. EQ-5Dc. Return to normal activitiesd. Pain VAS

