8.2 Anticipated Adverse Events (AEs)

All expected adverse events are listed in each device's IFU. Potential complications associated with interventional procedures, access, and device are described per each site's

standard of care pre-procedure consenting. Since this observational registry does not include any investigational devices or procedures, anticipated AEs are only specified in the IFUs, not in the protocol.

There may be additional unforeseen adverse events.

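### The primary safety evaluation has no device-relatedness condition, but Section 8 collects only adverse events at least possibly related to a Terumo device, so some primary events need not be recorded

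*Combined protocol and SAP*

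**What the plan says.** Section 3.2.1 sets the endpoint: "The primary safety evaluation is freedom from major adverse events and radial access complications within 30 days post-procedure". Major adverse events are death, MI and stroke. The second list opens with "Radial Access related complications are defined as" and covers radial artery occlusion, hand ischemia, arteriovenous fistula, pseudoaneurysm and complications that need surgical or endovascular intervention within 30 days. The synopsis lists the same components and words the second group as "Freedom from radial access related complications at 30 days". The only qualifier is a relation to radial access. Neither place asks for a relation to a device.

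The opening of Section 8 sets the collection rule: "Subject complications will be monitored via the reporting of device related adverse events occurring from the time of enrollment". It adds that "adverse events collected will be limited to any events possibly, probably or definitely related to a Terumo device", with relatedness "as described below in Section 8.2". Section 8.2, however, deals with anticipated events and says that "anticipated AEs are only specified in the IFUs, not in the protocol". The relatedness levels are in Section 8.4.

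The same limit appears in the reporting duty of Section 8.3, in the adverse event rows of Table 2 and the synopsis schedule, and in the description of the 30-day visit in Section 7.6.2. That section makes only the quality of life questionnaire mandatory. Section 7.7 is looser: "complications and/or device related adverse events will be collected on the eCRFs provided by the Sponsor".

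**The concern.** The endpoint and the rule that feeds it have different scopes. A site that follows Section 8 exactly can leave out events that Section 3.2.1 counts. Section 13.5 restricts analysis to observed cases but does not say whether a subject with no report is event-free or missing. If silence is read as event-free, the reported result is closer to freedom from Terumo-device-related events than to the endpoint as labelled, and the error runs in the favourable direction.

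Capture would also depend on each investigator's causality judgement. Section 13.4 presents the primary evaluations by site and tests for a site effect, so differences in attribution could look like differences in outcome. No hypothesis test or success threshold turns on this, but complication rates are part of the stated objective in Section 3.1.

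**Working it through.** **Step 1: each component against the route that the text requires.**

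| Component | Device relation needed to count? | Required route into the eCRF | What can be left out |
|---|---|---|---|
| Death | No | Study exit, with date of death (13.2.1) | Probably nothing |
| MI, stroke | No | Device-related adverse event report (8, 8.3) | Events judged unrelated |
| Radial access complications | No, only access-related | Access evaluations at the procedure visit (Table 2); after that, device-related adverse event report | Later events attributed to technique or a non-Terumo product |

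Neither schedule has a row for major adverse events or for radial complications after the procedure visit. Section 8.4 has no level for unrelated events, so the form of report it describes has no place for them.

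**Step 2: the plan's own figure.** Section 13.1 justifies 100 evaluable patients by a better than 80% chance of seeing at least one major complication at a rate of 1.6%.

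1 − (1 − 0.016)^100 = 1 − 0.984^100 = 80.07%

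The figure reproduces, with 0.07 points to spare, and it assumes that every such event is recorded. If only a share c is recorded, the chance is 1 − (1 − 0.016c)^100. The documents give no value for c, so this is an assumed range:

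| c | Chance of at least one recorded event |
|---|---|
| 1.00 | 80.07% |
| 0.90 | 76.6% |
| 0.75 | 70.1% |
| 0.50 | 55.2% |
| 0.25 | 33.0% |

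Section 13.1 does not define a major complication. Applying c to it assumes that these events pass through the same collection rule.

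**Step 3: effect on the reported rate.** One missed subject counted as event-free adds 1/n. The sizes come from Section 2.2: 100 subjects overall; 30% × 100 = 30 at a site at the cap; 100/10 = 10 per site on average if ten sites enrol. The event counts are illustrations, not figures from the documents. Intervals are exact (Clopper-Pearson) 95%.

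| n | True | Reported | Shift |
|---|---|---|---|
| 100 | 98/100 (93.0% to 99.8%) | 99/100 (94.6% to 100.0%), one missed | 1/100 = 1.0 point |
| 100 | 98/100 (93.0% to 99.8%) | 100/100 (lower limit 96.4%), two missed | 2/100 = 2.0 points |
| 30 | 29/30 (82.8% to 99.9%) | 30/30 (lower limit 88.4%) | 1/30 = 3.3 points |
| 10 | 9/10 (55.5% to 99.7%) | 10/10 (lower limit 69.2%) | 1/10 = 10 points |

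**The case against.** The strongest reply is that endpoint data and adverse event data are separate streams. The synopsis says that primary endpoint data are collected at 30, 180 and 365 days and that eCRFs hold the registry's evaluations. Radial artery occlusion has its own means of assessment there. Section 7.7 names complications alongside device-related events. Section 8.1 defines adverse events without a device condition and has each one assessed for seriousness, and Section 5.2 has the CRO tell the sponsor of serious events. On this reading Section 8 limits only the remaining adverse events.

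The reading is possible, but the text does not carry it. The synopsis lines give timing and medium, not content. Section 7.7 names neither MI nor stroke and sets no form or duty, and Section 8, directly after it, routes complications through device-related reporting. Section 8.1 defines events without requiring eCRF entry. The CRO relays serious events only as appropriate, and ethics committee notification under Section 5.3 is not data capture. The synopsis has investigators follow all adverse events, but again without requiring eCRF entry.

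Three parts of the objection stand and limit the size:

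- The lowest level in Section 8.4 takes in events thought unlikely to be caused by the device, and the filter covers any Terumo device, so many access events would pass.
- The eCRF cannot be seen and may already hold the fields.
- Section 13.5 does not say that silence means event-free, so the upward bias is conditional.

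**Conclusion.** The plan is wrong as written: the primary safety evaluation and the collection rule do not match, and the rule's cross-reference points to a section that does not define relatedness. The residual gap is an MI or stroke judged unrelated, or a radial access complication after the procedure visit attributed to something other than a Terumo device. Death is probably captured.

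That the texts conflict is certain. How many events would be lost is not known. The shifts of 1.0, 3.3 and 10 points are per missed subject, and they assume that subjects without a report are counted as event-free. If the eCRF already asks for these components irrespective of relatedness, the bias is zero and the repair is to wording only. The point should be fixed, but with no test or threshold depending on it, it does not undermine the registry as a whole.

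**What to change.** - Reconcile Sections 3.2.1, 7.6.2, 7.7, 8, 8.3 and 8.4, Table 2 and the synopsis, and change the Section 8 cross-reference from 8.2 to 8.4.
- Record each primary safety component on the eCRF at the 30-day contact as yes, no or unknown, with onset date, whatever its relation to a Terumo device. Keep the radial-access qualifier for the second list.
- Make device relatedness an attribute of the event and add a level for unrelated events.
- Compute primary safety from all such events with onset within 30 days, and state in Section 13.5 that unknown status is missing, not event-free.
- Leave assessment of radial artery occlusion to site standard of care, and report how many subjects were assessed.
- Keep the device-related limit for all other adverse events.

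The cost is a protocol amendment with IRB/EC notification and one eCRF page if the fields are not already there. No visits or tests are added, but the 30-day contact gains a required item besides the quality of life questionnaire. The reported rates may be slightly less favourable, and fewer subjects may be evaluable.
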